#### 12.4.3. Rationale for the Sub-Study A Combination

See [Section 2.1](#) for the overall study rationale in the master protocol.

Combinations of a BRAF inhibitor with a MEK inhibitor have become a standard in the treatment of participants with BRAFV600-mutant melanoma and NSCLC. Clinical and preclinical data suggests that the combination of a BRAF inhibitor such as encorafenib with a MEK inhibitor, such as binimetinib, will promote an anti-tumor immune response in BRAFV600-mutant tumors. Clinical and preclinical evidence also suggest that combining

encorafenib and binimetinib with a PD-1 blocking monoclonal antibody, will lead to deeper and more sustained anti-tumor control. Therefore, in this sub-study, a triplet combination of sasanlimab, encorafenib, and binimetinib will be evaluated to assess safety and clinical activity in participants with advanced/metastatic NSCLC.

#### **12.4.4. Justification for Dose in Sub-Study A**

##### **12.4.4.1. Starting Dose for Phase 1b**

The starting dose of sasanlimab in Sub-Study A is 300 mg Q4W and will remain constant throughout the study. Refer to master protocol [Section 4.3](#) for the justification for this starting dose.

The starting dose level for encorafenib is 300 mg QD and binimetinib is 45 mg BID in combination with sasanlimab. This corresponds to 1 dose level below the labeled doublet dose of 450 mg QD encorafenib and 45 mg BID binimetinib for metastatic melanoma. A subanalysis of the COLUMBUS trial indicated that this dose level was associated with improved tolerability over the 450 mg QD encorafenib and 45 mg BID binimetinib dose level along with comparable clinical activity.

##### **12.4.4.2. Criteria for Dose Escalation/De-Escalation**

Refer to [Section 12.10.6](#) for criteria for dose escalation/de-escalation via BLRM for Sub-Study A.

##### **12.4.5. Dose Limiting Toxicity**

Refer to master protocol [Section 4.3.3](#) for the definition of DLT.

The DLT observation period is the first 28 days starting with the first dose of any study drug in the combination.

##### **12.4.6. Maximum Tolerated Dose**

A dose level combination is a potential candidate for being the MTD level when all the following criteria are met:

- $\geq 6$  participants have been treated at that dose;
- Probability of target dosing  $> 50\%$ ; and
- Probability of overdosing  $< 25\%$ .

##### **12.4.7. Recommended Phase 2 Dose (RP2D) Definition**

Refer to master protocol [Section 4.3.5](#).

## 12.5. Study Population for Sub-Study A

Participants must meet all of the general inclusion and exclusion criteria as specified in the master protocol ([Section 5](#)) plus the following Sub-study A specific inclusion and exclusion criteria.

### 12.5.1. Inclusion Criteria for Sub-Study A

#### Phase 1b and Phase 2:

14. BRAFV600E mutation in tumor tissue or plasma as determined by a local laboratory assay and documented in a local pathology report. Other Class 1 BRAFV600 mutations (eg, V600K, V600D, and V600R) will be permitted by prior discussion with the sponsor. Only PCR or NGS-based local assay results will be acceptable.

15. Able to swallow, retain, and absorb oral medications.

#### Phase 1b only:

16. Any line of therapy for locally advanced/metastatic NSCLC. For Stage IIIB, disease relapse during treatment or within 6 months of chemoradiation with durvalumab consolidation will be considered metastatic disease.

#### Phase 2 only:

17. Previously untreated for locally advanced/metastatic NSCLC.

18. Able to provide a sufficient amount of plasma and tumor (primary or metastatic, archival or newly obtained); approximately 15 slides (minimum of 10 slides) or block are required.

### 12.5.2. Exclusion Criteria for Sub-Study A

#### Phase 1b only:

17. Receipt of anticancer medications or investigational drugs within the following intervals before the first dose of study intervention:

- a. ≤14 days for chemotherapy, targeted small-molecule therapy, radiation therapy, or antineoplastic biologic therapy.
- b. ≤14 days or 5 half-lives (minimum of 14 days) for investigational agents or devices. For monoclonal antibodies, <28 days from the last dose.

#### Phase 2 only:

18. Prior therapy with anti-PD-1, anti-PD-L1, or anti-PD-L2 agents.

### **Phase 1b and Phase 2:**

19. Participants who have documentation of any of the following: activating EGFR mutation (mutations located in exons 18-21), ALK fusion oncogene, or ROS1 rearrangement. Testing for EGFR mutation is required if status is unknown.
20. Prior treatment with any BRAF inhibitor (eg, dabrafenib, vemurafenib, XL281/BMS908662, etc) or MEK inhibitor (eg, trametinib, cobimetinib, selumetinib, RDEA119, etc).
21. History or current evidence of RVO or current risk factors for RVO (eg, uncontrolled glaucoma or ocular hypertension, history of hyperviscosity or hypercoagulability syndromes).
22. Concurrent or anticipated use of a non-topical medication known to be a strong/moderate CYP3A4 inhibitor or CYP3A inducer within 7 days prior to first dose of study intervention and throughout study duration.
23. LVEF <50% as determined by MUGA or echocardiogram.
24. Triplicate average baseline QTcF >450 msec for male participants or QTcF >470 msec for female participants or QTcF >480 msec in participants with right bundle branch block or a history of prolonged QT syndrome.

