**5. STUDY POPULATION**

This study can fulfill its objectives only if appropriate participants are enrolled. The following eligibility criteria are designed to select participants for whom participation in the study is considered appropriate. All relevant medical and nonmedical conditions should be taken into consideration when deciding whether a particular participant is suitable for this master protocol and sub-studies.

Prospective approval of protocol deviations to recruitment and enrollment criteria, also known as protocol waivers or exemptions, is not permitted.

Pfizer will review eligibility criteria verified by the investigator or qualified designee to confirm that participants meet study eligibility criteria before they are enrolled into the study. The enrollment approval process will be initiated for a participant after an informed consent

document has been signed and the investigator or qualified designee has assessed the participant as eligible. The enrollment approval will be based on review of CRF/system data or other site documentation.

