## 5.2. Exclusion Criteria

Participants are excluded from the study if any of the following master protocol criteria apply, as well as sub-study specific exclusion criteria provided in the respective sub-study appendices:

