### Medical Conditions:

1. Active or prior autoimmune disease that might deteriorate when receiving an immunostimulatory agent. Participants with diabetes type I, vitiligo, psoriasis, or hypothyroid or hyperthyroid disease not requiring immunosuppressive treatment are eligible.
2. Previous Grade  $\geq 3$  irAE; or unresolved irAEs prior to first dose of study intervention.
3. Active non-infectious pneumonitis, pulmonary fibrosis, or known history of immune-mediated pneumonitis.
4. Active infection requiring systemic therapy.

5. Clinically significant cardiovascular diseases, including any of the following:
  - a) History of acute myocardial infarction, acute coronary syndromes (including unstable angina, coronary artery bypass graft, coronary angioplasty or stenting)  $\leq 6$  months prior to start of study treatment;
  - b) Congestive heart failure requiring treatment (New York Heart Association Class  $\geq 2$ );
  - c) Uncontrolled hypertension defined as persistent systolic blood pressure  $\geq 150$  mmHg or diastolic blood pressure  $\geq 100$  mmHg despite optimal therapy;
  - d) History or presence of clinically significant or uncontrolled sustained cardiac arrhythmias (including uncontrolled atrial fibrillation or uncontrolled paroxysmal supraventricular tachycardia);
  - e) History of thromboembolic or cerebrovascular events  $\leq 3$  months prior to the first dose of study treatment. Examples include transient ischemic attacks, cerebrovascular accidents, hemodynamically significant (ie, massive or sub-massive) deep vein thrombosis or pulmonary emboli.  
*Note:* Participants with either deep vein thrombosis or pulmonary emboli that do not result in hemodynamic instability are allowed to enroll as long as they are stable, asymptomatic and on stable anticoagulants for at least 2 weeks.  
*Note:* Participants with thromboembolic events related to indwelling catheters or other procedures may be enrolled.
6. Other malignancy within 2 years prior to the first dose of study intervention, except for adequately treated basal cell or squamous cell skin cancer, or carcinoma in situ of the breast or of the cervix, or low-grade (Gleason 6 or below) prostate cancer on surveillance without any plans for treatment intervention (eg, surgery, radiation, or castration) or other concurrent malignancy investigator feels has a very low likelihood to become metastatic.

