7. Clinically significant multiple or severe drug allergies, intolerance to topical corticosteroids, or severe post-treatment hypersensitivity reactions (including, but not limited to, erythema multiforme major, linear immunoglobulin A [IgA] dermatosis, toxic epidermal necrolysis, and exfoliative dermatitis).
8. Symptomatic brain metastasis: participants previously treated for this condition or untreated with brain metastases  $< 10$  mm without associated edema, who are asymptomatic in the absence of corticosteroid therapy are allowed.
9. Leptomeningeal disease.
10. Known history of acute or chronic pancreatitis.
11. Concurrent neuromuscular disorder that is associated with the potential of elevated CK (eg, inflammatory myopathies, muscular dystrophy, amyotrophic lateral sclerosis, spinal muscular atrophy).

12. Other medical or psychiatric condition including recent (within the past year) or active suicidal ideation/behavior or laboratory abnormality that may increase the risk of study participation or, in the investigator's judgment, make the participant inappropriate for the study.
13. Participants with active, uncontrolled bacterial, fungal, or viral infection, including HBV, HCV, or known HIV infection. If HIV infection status is unknown, testing for HIV must be performed at sites where mandated locally.

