## 10.7. Appendix 7: ECG Findings of Potential Clinical Concern

ECG Findings That May Qualify as AEs

• Marked sinus bradycardia (rate <40 bpm) lasting minutes.

• New PR interval prolongation >280 msec.

• New prolongation of QTcF to >480 msec (absolute) or by <math>\geq 60</math> msec from baseline.

• New-onset atrial flutter or fibrillation, with controlled ventricular response rate: ie, rate <120 bpm.

• New-onset type I second-degree (Wenckebach) AV block of >30 seconds' duration.

• Frequent PVCs, triplets, or short intervals (<30 seconds) of consecutive ventricular complexes.

ECG Findings That May Qualify as SAEs

• QTcF prolongation >500 msec.

• New ST-T changes suggestive of myocardial ischemia.

• New-onset left bundle branch block (QRS >120 msec).

• New-onset right bundle branch block (QRS >120 msec).

• Symptomatic bradycardia.

• Asystole:

• In awake, symptom-free patients in sinus rhythm, with documented periods of asystole <math>\geq 3.0</math> seconds or any escape rate <40 bpm, or with an escape rhythm that is below the AV node;

• In awake, symptom-free patients with atrial fibrillation and bradycardia with 1 or more pauses of at least 5 seconds or longer;

• Atrial flutter or fibrillation, with rapid ventricular response rate: rapid = rate >120 bpm.

• Sustained supraventricular tachycardia (rate >120 bpm) ("sustained" = short duration with relevant symptoms or lasting >1 minute).

- Ventricular rhythms >30 seconds' duration, including idioventricular rhythm (heart rate <40 bpm), accelerated idioventricular rhythm (HR 40 bpm to <100 bpm), and monomorphic/polymorphic ventricular tachycardia (HR >100 bpm (such as torsades de pointes)).
- Type II second-degree (Mobitz II) AV block.
- Complete (third-degree) heart block.

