**Hemorrhage:** Hemorrhage occurred in 19% of participants, with events  $\geq$  Grade 3 occurring in 3.2% of participants. Fatal intracranial hemorrhage in the setting of new or progressive brain metastases occurred in 1.6% of participants. The most frequent hemorrhagic events

were gastrointestinal, including rectal hemorrhage (4.2%), hematochezia (3.1%), and hemorrhoidal hemorrhage (1%).

**Venous thromboembolism:** Occurred in 6% of participants, including 3.1% of participants who developed pulmonary embolism.

**Ocular toxicities:** Serous retinopathy is a class effect of MEK inhibitors. It is generally asymptomatic or mildly symptomatic and reversible. Serous retinopathy occurred in 20% of participants. Symptomatic serous retinopathy occurred in 8% of participants with no cases of blindness. The median time to onset of the first event of serous retinopathy (all grades) was 1.2 months. RVO is a known class-related adverse reaction of MEK inhibitors and may occur in participants treated with binimetinib in combination with encorafenib. In participants with BRAF mutation-positive melanoma across multiple clinical trials, 0.1% of participants experienced RVO.

**Pneumonitis/Interstitial Lung Disease:** Pneumonitis occurred in 0.3% of participants with BRAF mutation-positive melanoma across multiple clinical trials.

**Hepatotoxicity:** The incidence of Grade 3 or 4 increases in liver function laboratory tests was 6% for ALT, 2.6% for AST and 0.5% for alkaline phosphatase. No participant experienced Grade 3 or 4 serum bilirubin elevation.

**CK Elevation/Rhabdomyolysis:** Asymptomatic elevations of laboratory values of serum CK occurred in 58% of participants. Rhabdomyolysis was reported in 0.1% of participants with BRAF mutation-positive melanoma across multiple clinical trials.

**QTc Prolongation:** QT prolongation has been observed in participants treated with BRAF inhibitors. Encorafenib is associated with dose-dependent QTc interval prolongation in some participants. In the COLUMBUS study, an increase in QTcF to >500 msec was measured in 0.5% of participants.

**Embryo-Fetal Toxicity:** Encorafenib or binimetinib can cause fetal harm when administered to pregnant women.

Detailed information regarding clinical safety is presented in the respective IBs for encorafenib and binimetinib.

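### Sub-Study A exclusion criterion 24, as ordinarily read, gives participants with a known QT history the loosest QTcF entry limit before a QT-prolonging drug

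*Protocol*

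**What the plan says.** Section 12.5.2, criterion 24, applies to both phases of Sub-Study A. It uses the triplicate average baseline QTcF and excludes men above 450 msec, women above 470 msec, and, in a third clause, those above 480 "msec in participants with right bundle branch block or a history of prolonged QT syndrome". The clauses are joined by *or* in one sentence. There is no exception wording, no sub-numbering, and no statement that the third limit replaces the first two or adds to them.

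On the drug, Section 12.2.2.1 states: "Encorafenib is associated with dose-dependent QTc interval prolongation in some participants".

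The nearest other exclusions are in Section 5.2. Criterion 5d concerns "History or presence of clinically significant or uncontrolled sustained cardiac arrhythmias". Criterion 12 is a general clause for conditions "that may increase the risk of study participation" or that make the participant unsuitable in the investigator's judgment. Neither names a QT history or sets a QTcF limit.

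Section 5 has the sponsor review eligibility "to confirm that participants meet study eligibility criteria before they are enrolled into the study", and says that prospective approval of deviations from the entry criteria, "also known as protocol waivers or exemptions, is not permitted".

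**The concern.** A QTcF entry limit for a drug with a known QT effect should be at least as strict for people with a QT history as for everyone else. Here the history sits beside right bundle branch block in the clause with the highest limit. A higher limit for right bundle branch block need not signal greater QT risk at entry. A prolonged QT history is itself a QT risk factor, and the protocol gives no reason for relaxing the limit because of it.

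At stake is who may start encorafenib, and from what baseline. Because waivers are barred, the wording of the criterion has to give the answer.

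**Working it through.** No figure in the plan has to be reproduced. The check is to apply the criterion under each reading and compare it with the on-treatment QTc rules.

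**Inputs.** Entry limits of 450, 470 and 480 msec (Section 12.5.2, criterion 24). On-treatment rules for encorafenib (Section 12.10.4): above 500 msec with a rise of at most 60 msec from baseline, interrupt and resume one dose level lower, stopping permanently at the third occurrence; above 500 msec with a rise of more than 60 msec, stop permanently at once.

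**Ordinary reading.** The 480 msec limit replaces the sex-specific limit in the named subgroup. This gives every clause a function. The allowance is 480 − 450 = 30 msec for men and 480 − 470 = 10 msec for women.

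**Literal reading.** Each clause excludes independently. Anyone above 480 msec is already above 450 or 470, so the third clause removes nobody further. This is conservative but leaves the clause without purpose.

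**Decisions for a participant with a QT history:**

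| Participant | Ordinary reading | Literal reading |
|---|---|---|
| Man, 440 msec | eligible | eligible |
| Man, 460 msec | eligible | excluded |
| Woman, 460 msec | eligible | eligible |
| Woman, 475 msec | eligible | excluded |
| Either sex, above 480 msec | excluded | excluded |

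The readings differ only in the bands above 450 and up to 480 msec (men) and above 470 and up to 480 msec (women).

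**Link to the on-treatment rules.** Distance from the entry limit to the 500 msec interruption threshold: 500 − 450 = 50, 500 − 470 = 30 and 500 − 480 = 20 msec. QTcF above which a single event forces permanent discontinuation, which needs both more than 500 msec and a rise of more than 60 msec: 450 + 60 = 510, 470 + 60 = 530 and 480 + 60 = 540 msec. A higher permitted baseline shortens the distance to interruption and raises the absolute value at which one event ends treatment.

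**Does another section decide?** Criterion 5d turns on arrhythmia, not QT history. Criterion 12 may lead an investigator to exclude such a person but sets no QTcF rule. Sub-Study B, criterion 25 (Section 13.5.2), uses a single 480 msec limit with no subgroups, in a regimen without encorafenib, so it does not interpret criterion 24. Sponsor review may make decisions uniform across sites, but it does not say which limit the reviewer should apply.

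**The case against.** The strongest answer is that the criterion has one sensible meaning (450, 470, or 480 msec for the named subgroup) and that what remains is disagreement with a clinical threshold. The protocol accepts 480 msec for everyone in Sub-Study B, and nothing in it shows that 480 msec is unsafe. The risk is also managed: triplicate ECGs at Screening and Cycle 1 Day 1 and repeated single ECGs afterwards (Table 5), over-reading and repeat ECGs for large changes (Section 8.2.3), dose interruption and discontinuation (Section 12.10.4), no re-escalation of encorafenib after a reduction for QTcF of 501 msec or more (Section 12.6.6.2), and criterion 12 as a backstop.

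Most of this stands as mitigation. It does not answer the point: the more sensible the ordinary reading is, the more clearly the criterion favours the group with a known QT history. The safeguards act after entry or rest on judgment.

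Three stronger claims might be inferred and are not supported:

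- *That the history excludes by itself, so that a third rule competes with the other two.* Grammatically the history shares the 480 msec limit with right bundle branch block. Exclusion may have been the intent, but the sentence does not say so.
- *That Section 5.2 settles the matter in favour of the literal reading.* Its rule, "Participants are excluded from the study if any of the following master protocol criteria apply", works across numbered criteria. It does not say how clauses inside one criterion combine.
- *That someone entering at 480 msec already stands at an adverse-event threshold.* The Section 10.7 item containing "480 msec (absolute) or by" concerns newly arising prolongation above that value, and only as something that may qualify as an adverse event. A pre-existing 480 msec is neither new nor above it.

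**Conclusion.** The point holds in limited form. On its ordinary reading, criterion 24 loosens the QTcF limit by 30 msec (men) or 10 msec (women) for participants with a known QT history before a drug with a stated dose-dependent QTc effect. On the literal reading the clause does nothing. No other section chooses between them.

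The conclusion rests on taking the ordinary reading as the one a site would use, and on the absence of any stated reason for including the history in the allowance. The protocol gives no prevalence for either condition, so the number affected among the roughly 80 Sub-Study A participants cannot be estimated; it is probably small. The overall rate of QTcF above 500 msec reported from COLUMBUS does not help, because it describes a whole trial population and not this subgroup. No statistical figure is affected. This is a safety and eligibility correction that should be made, not a threat to the trial's inference.

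**What to change.** Take the history out of the 480 msec clause and state what replaces what. For example: *Triplicate average baseline QTcF >450 msec (male) or >470 msec (female); in participants with right bundle branch block and no history of prolonged QT syndrome, >480 msec applies instead.*

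Then state how the history is handled. At a minimum, hold these participants to the sex-specific limit, with or without right bundle branch block. If exclusion was the intent, list the history as a separate criterion. Deleting the phrase alone would leave a participant with both conditions inside the 480 msec allowance.

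**Cost.** One reworded sentence and one added line, with no new assessment, because the triplicate ECG is already scheduled. Against the ordinary reading, a few participants with a QT history above 450 to 480 msec (men) or above 470 to 480 msec (women) no longer qualify. Against the literal reading, the wording admits participants in those bands who have right bundle branch block and no QT history; if that allowance was not meant either, remove the 480 msec clause. A separate exclusion for the history would lose those participants at any QTcF.

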### **12.6. Study Intervention for Sub-Study A**

#### **Study Treatments:**

For purposes of this sub-study, study intervention refers to sasanlimab, encorafenib, and binimetinib. The prefilled syringe of sasanlimab is a medical device. Refer to [Section 6.1.1](#) for details about the administration of sasanlimab.

Participants will receive the following study treatments in each 28-day cycle:

#### **Phase 1b Dose Levels:**

Sasanlimab SC, 300 mg (150 mg/mL, 2 mL) prefilled syringe on Day 1 of each cycle

Encorafenib: 300 mg (4 × 75 mg oral capsules) QD (Dose levels 0 and -1), Encorafenib 450 mg (6 × 75 mg oral capsules) QD (Dose level 1).

Binimetinib: 30 mg (2 × 15 mg oral tablets) BID (Dose level -1), 45 mg (3 × 15 mg oral tablets) BID (Dose levels 0 and 1).

**Phase 2 Dose Levels:**

RP2D/MTD of sasanlimab 300 mg + encorafenib + binimetinib

